#### **5.1.4 Exit Visit**

***Note: All VA measurements MUST be made using a phoropter.***

- a. Indicate status of the subject on the Subject Exit Form. If the status is “Discontinued” or “Non-dispensed,” indicate the PRIMARY exit reason for each eye on the Subject Exit Form.
- b. Collect changes in ocular medical history and concomitant medications
- c. For all subjects, complete an exit ocular examination without lenses on the eyes. Collect the following assessments:
  - Spherocylindrical refraction
  - High-contrast distance (OD, OS, OU) logMAR BSCVA
  - Keratometry

Compare the final visit high-contrast distance (OD, OS) BSCVA to the high-contrast distance (OD, OS) BSCVA obtained at the Screening/Dispensing Visit. If the VA has decreased by  $\geq 10$  letters, explain.

For each eye, compare the final visit keratometry readings to the Screening/Dispensing Visit keratometry readings. If there is a change of 1.00 D or more, explain.

- d. Collect/assess all AEs/ADEs, including serious or significant non-serious AEs.
- e. Collect all worn and unworn study lenses from the subject.

***Note: The Investigator must return all worn and unworn study lenses to the Sponsor in the return materials provided. All study contact lenses must be accompanied by a Product Accountability Log.***

- f. Complete the Investigator survey following the completion of the subject’s final study visit.
- g. Complete the Exit visit eCRFs.

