## **7.8 Additional Statistical Considerations**

### **7.8.1 Analysis Populations**

- The Full Analysis Set (FAS) will consist of all eligible, dispensed subjects or eyes.
- The Safety Set will consist of all dispensed subjects or eyes.

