### **2. Lens Fitting**

- Allow lens to equilibrate for at least 10 minutes before assessing fit and vision.
- Evaluate distance and near vision binocularly in normal room illumination.
- If vision at distance and near is satisfactory, dispense lenses.

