6.5 Statistical Methods

6.5.1 Data Sets Analyzed

The Full Analysis Set (FAS) will consist of all eligible, dispensed subjects or eyes. If only one eye is dispensed, the subject will be included in the FAS for subject level analyses, but only the dispensed eye will be included in the FAS for eye level analyses. The FAS will be used for all efficacy analyses in subject level and eye level data.

The Safety Analysis Set will consist of all dispensed subjects or eyes. If only one eye is dispensed, the subject will be included in the Safety Analysis Set for subject level summaries, but only the dispensed eye will be included in the Safety Analysis Set for eye level summaries. All safety analyses and summaries will be based on the Safety Analysis Set.

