6.5.12 Safety Analyses

6.5.12.1 Adverse Events

All adverse events occurring during the study will be recorded and classified to below categories on the basis of MedDRA terminology, the number and percentage of each category will be summarized.

- AEs (NOT Device Related)
- Serious Adverse Events (SAEs) (NOT Device Related)
- Adverse Device Effects (ADE) (Device Related)
- Unanticipated Serious Adverse Device Effects (USADE) (Device Related)
- Anticipated Serious Adverse Device Effects (ASADE) (Device Related)

A treatment-emergent AE (TEAE) is defined as any AE with an onset on or after the date of the first study device use. If the start date of an AE is incomplete or missing, then the AE will be considered as a TEAE unless a partial date shows it as a pre-treatment event. All reported treatment-emergent AEs (TEAEs) will be summarized by the number of subjects reporting AEs, system organ class, preferred term, severity, seriousness, and relationship to study device.

Ocular Adverse events will be summarized as well by the number of subjects/eyes reporting AEs, system organ class, preferred term, severity, and relationship to study device. Ocular adverse events are defined as AEs specified in one or both eyes. Only treatment-emergent adverse events (TEAEs) are included in the summary.

If more than one AE is coded to the same preferred term for a subject, the subject will be counted only once for that preferred term using the most severe and most related occurrence for the severity and relationship to study intervention summaries, respectively.

If the severity of a TEAE is missing, the maximum severity will be assigned to the event for the summaries by severity. The value will be displayed as missing in the data listings.

If the relationship to the study intervention is missing for a TEAE, the event will be considered related to the study intervention for the summaries. The value will be displayed as missing in the data listings.

All information pertaining to AEs noted during the study will be listed by subject, detailing verbatim given by the investigator, preferred term, system organ class, start date, stop date, severity, actions taken, and device relatedness. The AE onset will also be shown relative (in

Page 31 of 44 – CONFIDENTIAL

number of days) to the day of initial use of the study device. In addition, a list of subjects who experienced SAEs will also be provided.

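### The Safety Analysis Set is defined by dispensing but TEAEs by first device use, so a subject or eye fitted with a study lens and not dispensed could have a TEAE that enters no safety summary table

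*SAP*

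**What the plan says.** The two documents agree on the safety population. SAP 6.5.1: "The Safety Analysis Set will consist of all dispensed subjects or eyes". Protocol 7.8.1: "The Safety Set will consist of all dispensed subjects or eyes". The SAP gives this set full scope: "All safety analyses and summaries will be based on the Safety Analysis Set". The planned tables numbered 14.3.x all carry it. When one eye is dispensed, the subject stays in at subject level, but "only the dispensed eye will be included in the Safety Analysis Set for eye level summaries".

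Treatment emergence has a different starting point. SAP 6.5.12.1: "A treatment-emergent AE (TEAE) is defined as any AE with an onset on or after the date of the first study device use". Protocol 7.2.1 says the same.

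The Fitting Guide (Protocol Appendix D) makes dispensing the result of an on-eye assessment. After the lens has settled for at least 10 minutes and vision has been checked: "If vision at distance and near is satisfactory, dispense lenses". Protocol 5.1.4 step a foresees exits without dispensing. For subjects whose status is discontinued or non-dispensed, the site must "indicate the PRIMARY exit reason for each eye on the Subject Exit Form".

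**The concern.** Two triggers for exposure are in use. Whether an event is treatment-emergent depends on device use; whether the person or eye is in the safety tables depends on dispensing. If use can come before dispensing, some exposed subjects or eyes can supply events that meet the TEAE definition but have no place in the summaries or their denominators.

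At stake is how completely the AE tables describe people who wore the investigational lens. Someone who reacts to the lens at fitting might be less likely to leave with a supply. If so, exclusion would depend partly on the outcome being counted. That is a plausible mechanism, and the documents neither state nor quantify it.

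**Working it through.** The plan gives no figure on this point to reproduce, so the check is mainly a tracing of definitions.

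**1. Can a study lens be on the eye before dispensing?**
- Protocol 4.0 supplies sites with both fit sets and dispensing sets of the kalifilcon A lens, so a fitting lens is a study lens.
- Appendix D (Initial Lens Power Selection, Criteria of a Well-Fitted Lens, and Multifocal Fitting Guidelines item 2) runs: place, wait, evaluate, then dispense if satisfactory.
- SAP 6.5.10.5.4 describes the final dispensed power as the one reached once fitting is finished.
- Protocol 5.1.1 step l names dispensing first and lists insertion, equilibration and refinement beneath it, but it also refers to the Fitting Guide.

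Neither document defines *dispensed*. The weight of the text favours fitting first.

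**2. Is dispensing separate from eligibility?** Protocol 5.1.1 step r, which comes after eligibility and insertion, limits ePRO registration to subjects who are both eligible and dispensed. The FAS in SAP 6.5.1 uses both conditions and provides for a subject with one dispensed eye. Dispensing is thus treated as its own condition.

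**3. Would an event at fitting be collected?** Yes. Protocol 6.2 makes AEs reportable from consent, and 5.1.1 step p assesses them at this visit.

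**4. Where would it be reported?**

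| Case | Wore a study lens | TEAE possible | In 14.3.x tables |
|---|---|---|---|
| Screened out before any lens | No | No | No (consistent) |
| Fitted and dispensed | Yes | Yes | Yes |
| Fitted, not dispensed | Yes | Yes | No |
| One eye dispensed, other eye fitted only | Yes, both eyes | Yes | Subject level yes; fitted-only eye not at eye level |

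The last two rows are the gap.

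**5. Illustrative size.** Let N be subjects fitted, k those not dispensed, d events among the dispensed and e events among the k, with at most one event per subject. The tables show d/(N − k); the rate in all exposed is (d + e)/N. I assume N = 300, the enrolment figure. This is generous, because Protocol 3.1 and 3.3 assign an ID at consent and treat that as enrolment, so 300 can include screen failures. Neither k nor e is given in the documents; the values below are assumptions.

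| k | d | e | Safety tables | All exposed |
|---|---|---|---|---|
| 0 | 6 | 0 | 6/300 = 2.00% | 6/300 = 2.00% |
| 3 | 0 | 1 | 0/297 = 0.00% | 1/300 = 0.33% |
| 15 | 0 | 2 | 0/285 = 0.00% | 2/300 = 0.67% |
| 3 | 6 | 3 | 6/297 = 2.02% | 9/300 = 3.00% |
| 30 | 6 | 3 | 6/270 = 2.22% | 9/300 = 3.00% |
| 30 | 6 | 0 | 6/270 = 2.22% | 6/300 = 2.00% |

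For the third row, the Clopper-Pearson 95% intervals are 0 to 1 − 0.025^(1/285) = 1.29% for 0/285, and 0.08% to 2.39% for 2/300.

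The tables understate the rate only when e/k exceeds d/(N − k). The last row goes the other way, and with k = 0 nothing changes.

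**The case against.** The strongest reply is that the gap may not exist. Protocol 5.1.1 step l is the operative visit procedure. It puts dispensing ahead of insertion, and step m then assesses the dispensed lenses. SAP 6.5.10.5.4 also refers to starting and final powers for dispensed lenses, which could mean that the starting lens already counts as dispensed. This stands as a possible reading. It does not settle the matter, because step l defers to a Fitting Guide with the opposite order.

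The non-dispensed exit status is weak evidence. Every consented subject receives an ID and counts as enrolled, so the status may cover only screen failures who never wore a lens. That also stands. No passage says that anyone is fitted and then not dispensed; the case rests on the definitions and on step 2 of the working.

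A reader might infer that such events vanish from the report. They do not. The AE listing in SAP 6.5.12.1 covers all AEs noted in the study with no restriction to the Safety Analysis Set, SAEs are listed too, and discontinuation reasons are tabulated for all enrolled eyes (Tables 14.1.3.1 and 14.1.3.2).

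A reader might also infer that the AE rate is biased downward. The documents give no fitting-failure rate and no link between reactions and non-dispensing. The Multifocal Fitting Guidelines make vision the condition for dispensing, step l directs refinement until vision is acceptable, and entrants are adapted multifocal wearers of at least 6 months. The direction and the size are both assumptions.

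**Conclusion.** The mismatch between the two definitions is in the text; its effect is conditional. If dispensing follows on-eye fitting, a fitted but non-dispensed subject, or at eye level a fitted but non-dispensed eye, can have a TEAE that is listed but enters no safety summary table or denominator. If dispensing is recorded before insertion, there is no gap.

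The size cannot be derived. In the illustrations with an event in a non-dispensed subject, the difference is between 0.33 and 0.98 percentage points (3.00% − 2.02%), but the counts are assumed and the true figure may be zero. Exposure at fitting is short, and the study tests no safety hypothesis. The primary test uses the FAS and is unaffected. This is a small inconsistency worth correcting because the correction is cheap.

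**What to change.** In SAP 6.5.1 and Protocol 7.8.1, define the Safety Analysis Set as all subjects or eyes on which a study lens, including a fitting lens, was placed, whether or not lenses were dispensed. Apply the same rule at eye level. Leave the FAS unchanged. The safety population then starts where the TEAE definition starts, and the order of events in step l no longer affects who is counted.

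The cost is one sentence in each document, plus two practical consequences:
- A few subjects with no follow-up data may enter the safety tables, so by-visit denominators will be smaller than the set.
- The site record must show lens placement for each eye of a non-dispensed subject. Step m of Protocol 5.1.1 lists assessments only for dispensed lenses, so a placement field may have to be added to the source document or eCRF.

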6.5.2 Endpoints at Scheduled and Unscheduled Visits

Efficacy and safety assessments conducted at unscheduled visits will be assigned to a corresponding scheduled visit if they occurred in a scheduled visit window (Table 1) and will be summarized by visit and visit type (scheduled or unscheduled). If subjects/eyes have multiple assessments at a given visit and visit type, each subject will be counted once for the worst case value for that visit and visit type. The exception to this rule is for continuous efficacy endpoints (including binocular lens VA in logMAR units and lens performance ratings), where the average over all of the multiple assessments for the visit and visit type will be summarized. A total column will be displayed to summarize data over unscheduled and scheduled visits using the same rule.

Page 13 of 44 - CONFIDENTIAL

Assessments done at unscheduled visit which occurs out of scheduled visit windows will only be included in the summary of all follow-up visits or all assessments; these data will not be windowed into a scheduled visit summary. Each subject will only be counted once in any given summary.

Data listings will present data from all visits.

Online consumer survey, investigator questionnaire, and treatment compliance will only be summarized using data from scheduled visits.

6.5.3 Disposition of Subjects

Disposition summaries will be presented for all enrolled subjects. These summaries will include an accountability of subjects, summarizing the number and percentage of subjects in the following categories: active subjects, eligible at the Screening Visit, and ineligible at the Screening Visit. A subject is considered active once enrolled until completing or discontinuing from the study. In addition, within the eligible and ineligible at baseline categories, the number and percentage of subjects who have completed the study and discontinued the study will be presented. Lens dispensation status will be presented for discontinued subjects. All percentages will be based on the number of subjects enrolled, except that dispensation status percentages will be based on the number of discontinued subjects. Subject status will also be summarized by investigational site.

Subjects and eyes in the Full Analysis Set and the Safety Analysis Set will be summarized as well, with percentages based on all enrolled subjects/eyes.

The reasons for study discontinuation will also be summarized for each eye. Only the primary reason for study discontinuation will be recorded. Percentages will be based on the number of eyes for all enrolled subjects.

Details of discontinued eyes and ineligible subjects will be presented separately. Subject listings will also be provided for disposition data, as well as analysis sets and inclusion/exclusion criteria.

6.5.4 Demographic and Other Baseline Characteristics

Demographic summaries will be presented for the FAS. Demographic characteristics including age (years), sex, ethnicity, and race will be summarized at the subject level. Age will also be summarized in the following categories: 40 - 49, 50 - 59, 60 - 69, 70+. Subjects reporting more than one race will be summarized as "Multiple." Sex, ethnicity, and race will

Page 14 of 44 – CONFIDENTIAL

be summarized as categorical variables, while age will be summarized as a continuous variable.

Baseline eye characteristic summaries will be presented as continuous statistics summary for the FAS. Diagnostic refraction sphere (diopters), cylinder (diopters) and add power (diopters) will be summarized at the eye level using minus cylinder notation. Positive cylinder will be converted to minus cylinder format by adding the cylinder power to the sphere power, changing the cylinder power sign from '+' to '-', and changing the axis by 90 degrees (adding 90 degrees if axis < 90 and subtracting 90 degrees if axis > 90). The mean refractive spherical equivalent (MRSE) (diopters) will be summarized as a continuous measure. MRSE is calculated after converting the sphere and cylinder to minus cylinder notation as MRSE = sphere measurement +1/2 of cylinder measurement. Axis (degrees) will also be summarized by frequency and percentages in category groups (0, 1 to 30 or 150 to 180, 31 to 59 or 121 to 149, 60 to 120). Pupil size (mm) will be collected at the Screening/Dispensing Visit and summarized continuously as well.

Subject listings for demographic and baseline eye characteristic data will also be presented.

6.5.5 Baseline Questionnaire

Each eligible subject will complete a questionnaire prior to study lens insertion. Responses will be regarding current habitual lens wear. The categorical responses will be summarized by frequency and percentage for the FAS. The denominator will be the number of subjects who have non-missing responses for each question in the baseline questionnaire. The numerical responses will be summarized continuously. In addition, the categories used for subgroup analysis will be presented together, refer to Section 6.5.11.5. Subject listings of responses will be presented.

6.5.6 Ocular Medical History and Lens/Lens Care History

Ocular Medical history and lens/lens care history will be collected at the Screening Visit.

The Medical Dictionary for Regulatory Activities (MedDRA) Version 25.1 will be used to code reported medical history terms. Ocular medical history will be presented in subject listings at the subject, eye, and event level by System Organ Class (SOC) and Preferred Term (PT).

Lens/lens care history will be assessed using collected data regarding subjects' most recent contact lens wear experience. Average number of days per week worn, average daily wear time, average hours of comfortable wear per day, and average number of times used

Page 15 of 44 - CONFIDENTIAL

rewetting drops per day for habitual rewetting drop users will be summarized at the subject level, and hours Lenses Worn on the Day of Screening/Dispensing Visit, if subject comes in to the study visit wearing a lens, will be summarized at the eye level using continuous summary statistics. A categorical summary of habitual rewetting drop users and non-users will be conducted with rewetting drop users defined as having an average number of times used rewetting drops per day collected at baseline > 0. Habitual lens sphere (diopters) will be summarized continuously at the eye level. In addition, routinely used pre-study contact lens care system will be summarized categorically at the subject level. Percentages will be based on the number of subjects with responses. The most recent lens correction brand will be summarized similarly by eye (OD, OS). Lens/lens care history data will also be presented in subject listings.

6.5.7 Concomitant Medications

All concomitant medications (ocular, systemic or topical) that have been taken in the past 30 days before signing the Informed Consent Form (ICF) and during the course of the study will be collected.

Medications will be coded using World Health Organization Drug Dictionary (WHO Drug Global C3, September 1, 2022) and presented using the therapeutic drug class (Anatomical Therapeutic Chemical (ATC) 4 classification) and preferred name. If the ATC 4 classification is not provided, the next lowest classification that is provided in the coding dictionary will be used. The preferred name will be defined as the active ingredient; if the active ingredient is not provided or includes more than two ingredients (e.g., multivitamins) then the drug name will be presented as the preferred name. Any uncoded terms will be presented with the ATC classification and preferred name of "Uncoded".

Reported and coded terms (ATC class and preferred name) will be presented in subject listings.

6.5.8 Measurements of Treatment Compliance

Treatment compliance will be assessed using lens wear parameter data.

Average number of days per week worn, average daily wearing time (hours), average hours of comfortable wear, and hours worn on the day at visit are collected at follow-up visits and summarized continuously at the eye level. Average number of days per week worn will also be summarized categorically at the eye level: 0, 1, 2, 3, 4, 5, 6, 7. Percentages will be based on the number of eyes with non-missing responses. Rewetting drop use (average number of times per day rewetting drops were used) will be collected and summarized continuously at

Page 16 of 44 - CONFIDENTIAL

the subject level for subjects who used rewetting drops at baseline only. Subjects who are habitual rewetting drop users with an on-treatment value of "not applicable" will be summarized as using 0 rewetting drops per day. In addition, the number and percentage of subjects who used rewetting drops at baseline will be presented.

Lens wear parameters will be presented in a data listing.

6.5.9 **Protocol Deviations**

Protocol deviation will be recorded throughout the study. Major deviations will be defined as any protocol deviations that could have an impact on the validity of the key outcomes in the study. Major protocol deviations will be identified in a review of the deviations by the study team prior to database lock. Major protocol deviations will be summarized in total for the Full Analysis Set. Subjects are only counted once under each protocol deviation category if more than one deviation occurred. A data listing of all protocol deviations will be provided.

6.5.10 Analysis of Efficacy

6.5.10.1 Descriptive Statistics

Analyses of effectiveness outcomes will be completed using the Full Analysis Set.

In general, data will be summarized by visit as appropriate. Data will be summarized separately at the subject and eye levels. For lens performance rating endpoints at the subject level, the worst case over both eyes will be derived and summarized for categorical variables.

Summaries for continuous variables will include the sample size (n), mean, standard deviation, median, minimum, and maximum. Means and medians will be presented with one more decimal place than the recorded raw data. Standard deviations will be presented with two more decimal places than the recorded raw data. Minima and maxima will be presented with the same number of decimal places as the recorded raw data. Values with magnitude less than one will be presented with a leading zero to the left of the decimal (e.g., 0.123 or -0.123).

Categorical data will be summarized using frequencies and percentages. Percentages will be presented with one decimal place. Percentages may not be presented when the count is zero. Unless otherwise specified, the denominator for percentages will be the number of non-missing values within the group being presented.

Page 17 of 44 - CONFIDENTIAL

